## V. STUDY PROCEDURES

### **Aim 1, and 1a Study Procedures:**

Modify Rules for Automated Diagnosis of CKD and Uncontrolled HTN: [name] is a participant in the NKDEP Health Information Technology care plan working group. She has contributed to their efforts to new national standards for diagnosis of patients with CKD using EHR data. We will modify the rules from the MAPLE study in order to align them with this new national standard. Then, we will create rules for automated diagnosis of uncontrolled hypertension. We will implement the BPA in “silent mode” for the control arm. This means that we will identify control patients in real time according to the same inclusion criteria as intervention patients, excluding all patients who are pregnant.

Develop Rules for Evidence-based Recommendations for HTN in CKD: We will leverage past work that we have done in a study that delivered recommendations based on JNC7. An example of one of the rules is to determine whether anti-hypertensive agents have been prescribed but are not at highest potency. If so, the CDS will deliver a recommendation to increase the dosage. Or, if multiple agents have been prescribed at maximum potency, the CDS will access the patient’s refill record. If the patient has not been refilling medications on schedule, the tool will recommend a medication adherence discussion. We will also include one-click access to documentation and orders relevant for CKD. For example, a message that gives a specific diagnosis, “This patient has stage 3b CKD with unknown level of albuminuria”), as well as an actionable order, “Click here to order a urine microalbumin to creatinine ratio test.” The BPA will include a BP entry field in which a PCP can record a repeat BP reading. If the PCP enters a BP reading, it will automatically be recorded in the vital signs flowsheet and vice versa. We will include appropriate laboratory monitoring test orders. Confirmatory testing is appropriate for an abnormal urine albumin level, so we will include an order if the prior result was abnormal. We will also provide one-click access to print patient handouts. In order to minimize cognitive overload and improve self-efficacy we will only deliver three messages at one time. We will develop a ranked list to drive the choice of recommendations. For example, in patients with CKD and HTN who smoke, tobacco cessation would be the highest priority.

Implementation of CDS in Epic: The next step is implementation in Epic as a BPA. Each of the rules will be added to the Epic database. The BPAs appear in an area of the screen that is visible when orders are being entered. Currently, there are several cancer screening BPAs and a seasonal influenza BPA. The CDS will be moved to the Production environment in “silent mode” before the scheduled start date of the trial, where it will record when it would fire, but it will not be displayed to the user. This step will allow us to validate that the rules are accurately identifying patients and producing the correct recommendations through a chart review. We will review 10 charts of patients with CKD and uncontrolled HTN per clinic for a total of 150 charts. The CDS will be activated in the Production environment on the start date of the clinical trial in Aim 2.

Validation of Hypertension-specific Process Measures: In preparation for the clinical trial in Aim 2, we will validate three process measures. Two of the measures will reflect treatment intensification by the PCP, 1) an increase in dosage or 2) addition of a new anti-hypertensive agent. The third measure will reflect medication adherence by the patient using data from a pharmacy benefits manager. We will perform a retrospective chart review of 150 charts to calculate the sensitivity and specificity of each rule.

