### III. SUBJECT SELECTION

**Subjects:** All patients over the age of 18 who have a visit with a PCP at one of the intervention practices during the 2 years preceding the study period will be eligible. We are able to utilize data from the past 2 years stored in the EHR to identify CKD patients with uncontrolled HTN. The first inclusion criteria will be CKD, defined as two prior eGFR  $16-59$  mL/min/1.73m $^2$  separated by 90 days, as calculated by CKD-EPI, or two prior UACR  $>30$ mg/g. The second inclusion criteria will be uncontrolled hypertension, defined as at least one SBP  $>140$  mmHg within the 2 years preceding the enrollment visit, as well as SBP  $>140$  mmHg at the enrollment visit. Our objective was to include PCPs who have a consistent panel of primary care patients. We obtained a list of currently employed physicians, physicians assistants and nurse practitioners in our primary care network of 15 practices. We excluded residents in training, as well as physicians who were only seeing urgent care and walk-in patients.

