### IV. SUBJECT ENROLLMENT

Randomization and Enrollment: This study will utilize a matched-pair cluster randomized design with the intervention on the cluster level, and the main outcome (6 month minus baseline change in SBP) measured at the patient level. We will have 174 clusters (made up of 185 clinicians) in the study. We will match pairs of clusters with similar number of patients and prior year mean blood pressure of patients in the cluster. One cluster in each pair will be randomized to the intervention and unit one to usual care. Patients will be electronically identified and included in the study over the course of 12 months. Patients seen by PCPs during the pilot study will be excluded. Retrospective data indicates that 70% of patients have a follow-up around 6 months. Outcomes assessment will occur at 180 days (+/- 60 days). After the 12-month enrollment period ends, data collection will continue for 6 months so that those enrolled toward the end of the enrollment period will have a full 6 months to complete any interventions ordered by the PCP. A small subset of PCPs will be enrolled in a pilot study for approximately one month, as described below in study procedures Aim 1b. Clinical outcomes will be recorded and reviewed every month over the course of the trial.

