**Specific Aim 2 & 2a Procedures:**

**Setting:** The Brigham and Women's Primary Care Practice-Based Research Network (BWPC PBRN) is one of 155 PBRNs nationally certified by the Agency for Healthcare Research and Quality (AHRQ). The BWPC PBRN is a network of 15 practices which includes hospital-based practices, community-based practices, and community health centers affiliated with Brigham and Women's Hospital. The network includes 185 primary care physicians that care for approximately 150,000 patients.

**Subjects:** All patients over the age of 18 who have a visit with a PCP at one of the intervention practices during the 2 years preceding the study period will be eligible. We are able to utilize data from the past five years stored in the EHR to identify CKD patients with uncontrolled HTN. The first inclusion criteria will be CKD, defined as two prior eGFR 16-59 mL/min/1.73m^2 separated by 90 days, as calculated by CKD-EPI, or two prior UACR >30mg/g. The second inclusion criteria will be uncontrolled hypertension, defined as at least two SBP >140 mmHg within the 2 years preceding the study period. We will exclude all patients who are currently pregnant. The CDS will review lab data starting five years before the visit to determine whether the patient has CKD using the logic described above. If the patient has CKD, the CDS will search BP data starting one year before the visit to determine whether the patient has had at least two SBP > 140 mmHg.

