## VII. RISKS AND DISCOMFORTS

There are minimal risks to physicians or patients as a result of the intervention. For clinicians, there is a risk that the decision support and other tools could have unexpected adverse consequences such as creation of more work, unfavorable workflow issues, and overdependence on technology. Although important to consider, these risks are balanced by evidence suggesting the effectiveness of computerized clinical decision support to improve the quality of patient care. For patients, the risks are those that are typically undertaken in the receipt of general medical care. That is, it is conceivable that the intervention could result in a change in management (e.g., ordering more tests, referral), but in the case of chronic kidney disease this may in fact lead to a clinical benefit. There also is the possibility of psychological risk to patients associated with being labeled as having chronic kidney disease; however, this risk is outweighed by the potential benefits associated with better evaluation and treatment of the disease. Finally, there is a risk of overtreatment of hypertension which may cause hypotension or an acute decrease in kidney function. The intervention is delivered to the primary care physician, who will weigh the risk and benefit of treatment intensification. However, this risk is expected to be low since we only recommend treatment intensification within consensus guidelines.

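### The plan gives conflicting blood-pressure triggers for the decision support, and one of them allows a dose-increase message at a visit where SBP is not above 140 mmHg

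*Combined protocol and SAP*

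**What the plan says.** All references are to the combined protocol and SAP.

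- **Section III, Subject Selection.** Uncontrolled hypertension means at least one SBP above 140 "mmHg within the 2 years preceding the enrollment visit, as well as SBP" above 140 mmHg at that same visit.
- **Section V, Specific Aim 2 & 2a Procedures, criterion.** It means at least two SBP above 140 "mmHg within the 2 years preceding the study period". Nothing is required of the reading at the visit.
- **Same paragraph, run-time logic.** Once CKD is confirmed, "the CDS will search BP data starting one year before the visit to determine whether the patient has had at least two SBP" above 140 mmHg. Again nothing is required of the current or latest reading.
- **Section V, Aim 1 and 1a Study Procedures, dose rule.** "An example of one of the rules is to determine whether anti-hypertensive agents have been prescribed but are not at highest potency". The consequence follows: "If so, the CDS will deliver a recommendation to increase the dosage". At most three messages are shown at a time, taken from a ranked list.
- **Same section, repeat reading.** "The BPA will include a BP entry field in which a PCP can record a repeat BP reading". The entry is filed to the vital signs flowsheet. No effect on the message is stated.
- **Section VII, Risks and Discomforts.** Overtreatment, with hypotension or an acute fall in kidney function, is acknowledged, but "this risk is expected to be low since we only recommend treatment intensification within consensus guidelines". The section also relies on the PCP to balance benefit against harm.

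**The concern.** The condition that makes a patient eligible and the condition that makes a dose-increase message appear are two different things, and the plan does not separate them. Where it comes closest to specifying the tool's run-time behavior, the blood-pressure test looks back over a year and the dose rule looks at the regimen. Neither looks at the SBP of the visit at which the advice is given.

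At stake is advice to intensify treatment in a patient whose pressure is no longer above the plan's own 140 mmHg cut-off. Section VII itself names the harms that overtreatment could cause. The content of the message matters because the design is meant to move behavior: under Aim 1c, intervention PCPs are asked to commit to the recommendations or to record why they depart from them, although the pledge they sign is worded more softly, as one to consider the advice.

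**Working it through.** The plan states no figure on this point, so there is none to reproduce. The check has three steps.

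**1. The conditions side by side**

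| Place | Blood-pressure condition | Is the SBP of the visit used? |
|---|---|---|
| Section III | One SBP >140 in the prior 2 years, plus SBP >140 at enrollment | Yes, at the enrollment visit |
| Aim 2 & 2a, criterion | Two SBP >140 in the 2 years before the study period | Not required |
| Aim 2 & 2a, run-time logic | Two SBP >140 in the year before the visit | Not required |
| Aim 1 and 1a, example dose rule | None stated (regimen only) | No |
| Aim 1 and 1a, repeat-reading field | Reading is recorded | No stated effect on the message |

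**2. One visit, following the Aim 2 & 2a logic as written**

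Take, for illustration, a CKD patient with two readings above 140 mmHg earlier in the year, treated since, at 112 mmHg today and on less than the maximum dose. The run-time condition is met by the two old readings. The example dose rule is met by the regimen. The message may therefore be shown, subject to the ranking and the three-message limit. Under Section III the same patient would not qualify at this visit, because 112 is not above 140. This conflict needs no assumption about repeat firing.

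**3. Later visits, assuming that the alert is evaluated again after enrollment**

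Inputs:
- look-back of one year, taken as 365 days (Aim 2 & 2a);
- one qualifying reading at enrollment, day 0 (Section III);
- the other qualifying reading D days earlier;
- outcome window of 180 days plus or minus 60, so 180 − 60 = day 120 to 180 + 60 = day 240 (Section IV).

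At a visit on day t, the older reading is t + D days old. Both readings are still inside the look-back if

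t + D ≤ 365, that is, D ≤ 365 − t.

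| Visit day t | Largest D that keeps the condition true |
|---|---|
| 120 | 365 − 120 = 245 days |
| 180 | 365 − 180 = 185 days |
| 240 | 365 − 240 = 125 days |

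The enrollment reading itself is inside the look-back throughout, since 240 ≤ 365. A patient with D of 125 days or less therefore meets the run-time condition over the whole outcome window, whatever the later readings are. The documents give neither the distribution of D nor the visit frequency, so the calculation shows that the case is possible, not how common it is.

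**The case against.** Several counter-arguments have force.

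- **Section III may govern the alert.** Section V says control patients are identified in real time by the same inclusion criteria as intervention patients, so the alert does apply inclusion criteria. If those are the ones in Section III, the enrollment visit is protected. That stands. But Aim 2 & 2a restates the criterion without the visit reading and adds its own run-time search, and nothing says which prevails. Section III also says nothing about later visits.
- **The dose rule is only an example.** This is true. The rules are still to be developed, a blood-pressure condition may be intended, and the message limit means that meeting a condition does not guarantee display. The claim is therefore that the text allows the message, not that it will appear.
- **Repeat firing is not stated.** A reader might infer that the tool will go on urging escalation at later visits. The search is keyed to the visit and no section limits the alert to one firing, but silence does not establish repeat firing. Step 3 of the check is conditional on it; step 2 is not.
- **The PCP decides.** A reader might infer that the rule contradicts Section VII. It does not. Section VII rests on guideline-concordant advice and on clinical judgment, and lists hypotension and loss of kidney function last, without ranking them as the principal risks.
- **Checks already exist.** There is a silent-mode review of 10 × 15 = 150 charts, PCP feedback at each firing in the pilot, monthly tabulation of low SBP, creatinine and potassium (Table 1), and yearly DSMB review of SBP below 110 mmHg (Section IX). These help. But the chart review samples patients with uncontrolled hypertension, so it is not described as testing patients whose SBP has come down, and neither the monthly outcomes nor the DSMB review links a low reading to a message shown.

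A reader might also infer that stale alerts would depress alert acceptance or explain a null result. The documents do not support that. Table 1 counts acceptance per patient, so a later override need not undo an earlier acceptance, and no route to a null SBP result is shown.

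**Conclusion.** The point holds as a conflict between stated rules with a possible safety consequence, and not merely as missing detail. Its core rests on the text alone: Section III and Aim 2 & 2a differ on whether the visit's own SBP must be high, and neither the example dose rule nor the repeat-reading field closes the gap. The extension into the outcome window rests on two assumptions, that the alert is evaluated after enrollment and that a year is 365 days. Its bounds are 245 days at day 120 and 125 days at day 240, with frequency unknown. For Section VII, the consequence is that its low-risk rationale lacks support in the trigger text. The primary analysis is not shown to be affected.

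**What to change.** Before go-live, reconcile Sections III, V (both the Aim 1 and 1a and the Aim 2 & 2a text) and VII. The revised text should state separately:

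1. the blood-pressure condition for enrolling a patient;
2. the blood-pressure condition, if any, for displaying a dose-increase message at a given visit;
3. whether the alert fires after enrollment;
4. how a repeat reading entered in the alert is handled, including one that is not above 140 mmHg.

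The clinical choice in each case belongs to the investigators; none is proposed here.

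In addition, use the alert log and the control-arm silent log to tabulate, by arm, the firings at which the visit SBP was not above 140 mmHg and those at which it was below 110 mmHg. Both cut-offs are the plan's own. Give the table to the DSMB. Silent mode is already described as recording when the alert would fire, so a two-arm table looks feasible. The team should confirm that the log also captures which message was, or would have been, shown.

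The cost is a small amount of rule-text work and one log-based table.

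### Only intervention PCPs are offered a repeat-BP field, and no rule fixes which reading, or which visit within the window, counts as baseline or follow-up SBP, so recorded SBP change could differ by arm without a true effect

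*Combined protocol and SAP*

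**What the plan says.** Section V (Aim 1, and 1a Study Procedures) describes the field: "The BPA will include a BP entry field in which a PCP can record a repeat BP reading". When a PCP uses it, "it will automatically be recorded in the vital signs flowsheet and vice versa". The same section has the BPA run silently "for the control arm. This means that we will identify control patients in real time according to the same inclusion criteria as intervention patients". The paragraph on implementation in Epic explains, for the pre-trial validation phase, that a silent BPA logs when it would have fired but is not shown to the user.

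Section IV gives the "main outcome (6 month minus baseline change in SBP) measured at the patient level" and sets outcome assessment at 180 days, plus or minus 60. It adds: "Retrospective data indicates that 70% of patients have a follow-up around 6 months". Table 1 in section VI lists the primary variable as mean SBP, analysed as change from baseline, at 6, 12 and 18 months. The controlled-SBP rate is secondary at the same times. Table 1 does not say whether the mean is over readings, visits or patients.

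The entry rule appears in two forms. Section III asks for one SBP above 140 mmHg "within the 2 years preceding the enrollment visit, as well as SBP" above 140 at that visit. The Subjects paragraph under Specific Aim 2 & 2a has uncontrolled hypertension "defined as at least two SBP >140 mmHg within the 2 years preceding the study period", and then has the decision support search BP data from one year before the visit.

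**The concern.** The intervention contains a device that can change how its own primary outcome is recorded. A repeat taken because the first reading was high will, on average, be lower through regression to the mean, even if the patient's pressure is unchanged. If such repeats are stored more often in one arm, and the analysis data set draws on them, the arms differ in measurement as well as in treatment.

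Regression to the mean between enrolment and 6 months is common to both arms and cancels in the comparison. An excess of same-visit repeats in one arm does not cancel. Neither a larger sample nor adjustment for clustering removes it. The controlled-SBP rate is exposed too, since a repeat can move a patient across the threshold. With the reading and visit left open, that choice could also be made after the data are seen.

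**Working it through.** **What is fixed and what is not.** The plan states no power calculation, target effect or SD, so there is no figure to reproduce.

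- Baseline: section III names an enrolment-visit SBP for eligibility but does not call it baseline.
- 6 months: days 120 to 240 (180 - 60 to 180 + 60). No rule picks among visits in this window.
- 12 and 18 months: listed in Table 1, with no window and no visit rule.
- Reading within a visit (first, last, lowest or mean): not stated for any time point.
- Source of outcome SBP: the flowsheet is implied, not stated.

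**Inputs, all assumed.** Single-reading SD 18 mmHg. Correlation r between two readings at one visit 0.75 to 0.9. Excess probability p that an intervention visit with a first reading above 140 has a stored repeat, 0.15 to 0.5. Underlying mean m of 142 to 150 at enrolment and 142 to 145 at 6 months. True effect zero. The last reading counts at any visit where repeats are stored.

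**Formulas.** With a = (140 - m)/18 and L = phi(a)/(1 - Phi(a)), the expected fall from first reading to repeat, given a first reading above 140, is (1 - r) x 18 x L.

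- Enrolment shift under the section III entry rule, where every enrolment reading exceeds 140: B = p x (1 - r) x 18 x L.
- 6-month shift, where only a share P = 1 - Phi(a) exceeds 140: F = p x P x (1 - r) x 18 x L.
- Intervention minus control difference in recorded change: B - F.

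**Worked values at r = 0.75, p = 0.5.**

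- Enrolment, m = 142: a = -0.111, L = 0.729, so B = 0.5 x 0.25 x 18 x 0.729 = 1.64.
- 6 months, m = 142: P = 0.544, so F = 0.544 x 1.64 = 0.89.
- 6 months, m = 145: P = 0.609, L = 0.630, so F = 0.5 x 0.609 x 0.25 x 18 x 0.630 = 0.86.

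**Results over the assumed ranges (mmHg; positive is against the intervention).**

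| Repeats that count | Regression to the mean alone | Extreme if repeats are also 5 mmHg lower (assumed) |
|---|---|---|
| Enrolment only | +0.1 to +1.6 | +4.1 |
| Both visits | +0.02 to +0.8 | +1.9 |
| 6 months only | -0.1 to -0.9 | -2.4 |

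The last row is the case where the qualifying first reading is baseline and the last reading is used at follow-up. Averaging first and repeat halves every entry. A lowest-reading rule gives somewhat larger values.

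A cruder check uses an excess repeat share of 0.3, a repeat 5 mmHg lower and half of patients still above 140 at 6 months. It gives 0.3 x 5 = +1.5 (enrolment only), -0.3 x 0.5 x 5 = -0.75 (6 months only) and 1.5 - 0.75 = +0.75 (both).

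**Controlled rate.** Table 1 gives no threshold. Taking control as 140 or below, the same inputs raise the intervention arm's rate by about 1 to 6 percentage points under a last-reading rule, from regression to the mean alone. This arises only if repeats occur at follow-up.

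**Under a first-reading rule at both visits,** stored repeats drop out and the same-visit artefact is 0.

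**The case against.** The strongest reply is that the bias needs several conditions, none of them stated: outcome SBP comes from the flowsheet, a rule other than first reading is used, and intervention PCPs record more repeats than controls. The field is an option, not an instruction. Control PCPs may re-measure and enter a value. Uptake is not given. A false gain also needs repeats at follow-up, and no text says the BPA fires again there. If the enrolment reading that qualifies the patient is used as baseline, the adverse enrolment figures vanish. All of this stands, and it limits the point to a risk of unknown sign and size.

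A reader might go further and infer that the design favours the intervention. The documents do not support that. The field is certain to be offered only when the BPA fires at enrolment, and repeats counted there work against the intervention.

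A reader might also infer that the outcome time points are wholly undefined. They are not: section IV gives a window and section III an enrolment-visit reading. What is missing is the selection rule inside the window and the visit. Nor does the text under Specific Aim 2 & 2a exclude a high reading at the current visit; it simply does not require one.

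The reply does not remove the omission, or the arm difference in what PCPs are shown.

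**Conclusion.** The point holds as a gap in the outcome definition combined with an arm asymmetry built into the intervention. It should be corrected before analysis; it is not a demonstrated bias. The artefact could mask an effect or mimic one, depending on a rule that the plan leaves open. The figures show what is possible under assumed inputs, not what is likely. They matter because the Background cites an average effect of only 1 mmHg for decision support, in a non-CKD population, and several of the assumed scenarios reach or pass that. Confidence is medium, since uptake of the field and firing at follow-up are unknown.

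**What to change.** For the primary SBP change and the controlled-SBP rate, prespecify one rule for both arms:

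- **Reading:** the first recorded SBP of the visit at baseline and at 6, 12 and 18 months. Exclude BPA-entered values and, where the BPA fires or would fire silently, any reading time-stamped after it. The time stamp is needed as well as the source, because a repeat can be typed straight into the flowsheet. At a visit where the BPA does not fire, the first recorded reading applies as it stands. State how a visit with no usable reading is handled.
- **Visit:** name the baseline visit, for example the enrolment visit, and the visit that counts at each later time point, for example the one closest to the target day, with a stated window at 12 and 18 months as well.
- **Reporting:** readings per visit by arm, and a sensitivity analysis using all readings.

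The entry rules in section III and under Specific Aim 2 & 2a, including the two-year and one-year look-backs in the latter, must be reconciled, because the size of any enrolment artefact depends on them.

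The cost is a few definition sentences, a filter on the EHR extract and one by-arm count. It assumes that silent firing times are kept for controls during the trial. The price is slightly more noise: SD 18 for one reading, against 18 x sqrt((1 + r)/2) = 16.8 to 17.5 for the mean of two under the assumed correlations. The rule removes the same-visit repeat artefact only. It does not address arm differences in who returns within the window, where about 70% are expected.
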